2.2 Primary outcome measures

As this is a qualitative study, there is no primary outcome measure. However, the aim is to present the experience, attitudes and values of staff and patients in narrative form (final report and publication) and in visual summary formats (infographics), to be shared across the relevant networks and contribute to the overall study aim of providing evidence for NHS decision makers on the use of single-use vs. multiple-use endoscopes in gastroenterology.

3 STUDY DESIGN AND METHODS OF DATA COLLECTION AND ANALYSIS

3.1 Study Design and Data Collection

This is a cross sectional qualitative study involving two methods of data collection. Data collection using both methods will be conducted in parallel.

Method 1: Semi-structured interviews with NHS patients.

NHS patients will be purposefully sampled to take part in semi-structured interviews. Screening will be done at site by the PI and/or research team. Patients will be approached either at their endoscopy appointment, where the study will be explained and documents shared with them, or by being sent the study information and documents in the post. They will be given at least 24 hours to decide if they'd like to participate.

Patients interested in taking part can contact the research team and express their interest via details provided on the PIS. Alternatively, they may be contacted by the research team after a reasonable amount of time has passed, to see if they have received and read the PIS and are interested in taking part.

Consent to participate will be obtained either in-person at an appointment or remotely by telephone by the PI or an appropriately qualified member of the research team at the site, before the interview is performed. An interview date will be arranged with the participant at a time and date that is acceptable to them. The interviews will be conducted by an experienced qualitative research team member, using a topic guide developed for this study, and last approximately 30-60 minutes.

Patients can choose whether they want to be interviewed via Microsoft Teams or by telephone. Participants will be made aware that the interviews will be recorded and professionally transcribed, and will be anonymised. Once the interview is complete the research team member will transfer the interview file to the secure university cloud storage. Interviews and demographic data will be pseudonymised prior to transcription and anonymised following the transcription.

Analysis will be conducted in parallel to data collection to allow for progressive focusing as the data collection progresses. Analysis will follow the steps of thematic analysis. Each file will be transcribed and checked for accuracy against the original file. Once accuracy is assured the audio/video files will be deleted.

Once analysis is complete, the transcripts containing raw data will be archived and stored on University secure storage. Aggregate anonymised data will be made available to the wider research team for report writing.

Translation and interpretation will be available for all persons who might not adequately understand verbal explanations. Translation and interpreters will be provided from across a network of support at UHCW and academic partners.

Method 2: Focus groups/Interviews with NHS staff.

NHS staff will be identified by the PI, or research team at each site and invited to take part via email or verbally in-person. They will be given the PIS and will have at least 24 hours to decide if they'd like to take part. A follow up email will be sent by the PI or research team after a reasonable amount of time has passed with no contact.

Consent to participate will be obtained in-person by the PI or an appropriately qualified member of the research team at site before the focus group. Focus groups of 2-5 people will be conducted virtually via Microsoft Teams by an experienced qualitative research team member. However, if this is not feasible due to time constraints, a one-on-one interview may be scheduled instead. Participants will be made aware that the focus groups/interviews will be recorded, anonymised and professionally transcribed.

Each focus group or interview may take 30-60 minutes to complete, during which participants will be asked questions according to a topic guide. Data handling, storage and analysis will follow the same procedure as for the interview data.

The topic guides for both interviews and focus groups will be used flexibly rather than tightly scripted. However, pre-work and discussion with patient contributors suggests that key questions will aim to understand staff and patients' perception of risk from reuse or disposal of equipment, and views about environmental impact of medical procedures.

The topic guide for both the interviews and focus groups will be informed by discussion with the patient contributor group, research team, and data collected in work packages 1-3.

3.2 Data Analysis

Qualitative data will be analysed in offices located at the University of Warwick (UoW) and University of Birmingham (UoB), using university computers. Both institutions will be used due to researchers changing affiliation during this project. Analysis will be supported using both Microsoft Excel and NVivo. Pseudonymised recordings will be sent to a transcription company who are preferred suppliers of our academic partners. Pseudonymised transcripts will be stored electronically on UoW and UoB servers on password protected files. Analysis will be conducted by a member of the research team, with support from the study collaborators.

Analysis will follow the steps of thematic analysis outlined by Braun and Clarke (2021) ^[44]. Analysis will begin with reading and rereading the data contained in the pseudonymised and transcribed interviews and focus groups. Transcripts will be cross-checked with the original recordings to ensure accuracy of the transcription. Transcripts will then be line-by-line coded by an experienced qualitative researcher and 10% will be independently coded by the Work Package lead. An initial coding frame (after 3-5 transcriptions) will be shared with the wider research team for feedback and cross checking of codes and meaning. Codes will be assembled into categories and themes using the One Sheet of Paper (OSOP) technique ^[45]. OSOP can be used when presenting stages of qualitative analysis back to the research team and stakeholder groups, who may not be experienced qualitative researchers.

Data from staff focus groups/interviews and patient interviews will be analysed separately, first by centre and then, by participant group. It is recognised that abstract lessons may be learnt from exploring the entirety of the data. Therefore, if appropriate, the patient and staff qualitative data will be compared, contrasted and combined, looking for consistencies and inconsistencies in the data and for deviant cases which require further investigation.

Initial findings will be shared in stakeholder consultation workshops with the Patient and Public Research Advisory Group (PPRAG) to capture the views of people who are invited to receive endoscopy, and second with the Green Endoscopy Network (which has international membership) and the British Society of Gastroenterology Endoscopy Committee. Where appropriate, the consultation feedback will be incorporated into our final qualitative findings (e.g., to help expand, or interpret themes) and subsequent recommendations, exploring how information provision for endoscopy could be better provided to people invited for endoscopy.

Findings will be reviewed in the context of equality, diversity and inclusion (ED&I) to investigate the impact of the work on different groups of people, for example, could the

results generate or contribute to inequalities in accessing procedures. Input from patient contributors to this study suggested that consideration could be given to the application of this work in resource poor settings. For example, it was asked “would single-use scopes prove more difficult to dispose of if the appropriate infrastructure were not in place?” Patient contributors were also interested in the usefulness of this work for other medical procedures - such as surgical instruments.

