While the scope of this study is limited to the endoscopes used in gastroenterology, the target is that the methods used to incorporate the views and experiences of patients and staff will be transferable, e.g. to other types of endoscopes and surgical equipment. Similarly, the systematic review (WP1) will search and synthesise literature to identify key considerations and the underlying mechanisms through which various factors may influence the choice between single-use and multiple-use devices, and how these vary by contextual characteristics of person and place. An important output of the project will be a novel system-based logic model ^[20] which depicts the extended endoscope life cycle in the broad ecosystem beyond clinical care pathways. This logic model will be informed by outputs from this study (as well as the other WPs) and will show the mechanisms by which single-use or multiple-use endoscopes influence effectiveness, cost-effectiveness, and environment, and will provide an evidence-based foundation to build on and promote sustainability and the transferability of research findings to other surgical equipment and areas of practice.

Endoscopy is a relatively invasive intervention from the perspective of patients. Patients know they are receiving endoscopy, and often know what the procedure involves and who might do it. However, little information is shared regarding the medical device (the scope) which the clinician uses to perform the intervention. Patients may not be aware that different types of endoscopes are available, with varying environmental profiles. This study is important to understand and work with the degree of risk people having endoscopy are willing to accept, and to understand what additional information people would like, in order

to feel satisfied with different endoscope options. It will be important to determine how the balance between infection control and environmental impact should best be communicated to people in accessible formats.

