1.3 Proposed study

This project is taking place as part of Work Package 4 (WP4, see Figure 1). A range of data collection methods will be used to discern the attitudes and experiences of NHS patients receiving endoscopy, and staff working in the NHS who handle colonoscopes and other GI endoscopes before and after use (e.g., selection, procurement, disinfection, and disposal of endoscopes).

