6. STUDY PROCEDURES

6.1 Sampling

6.1.1 Size of sample

No sample size calculation was derived as this is a qualitative study where we aim to maximally sample participants across the units (not depth of investigation at each unit). We will use maximum variation sampling based on the following parameters: age, ethnicity, gender for all participants, and years of experience for NHS staff.

Patients

We plan to interview 5 patients from 6 sites but recognise that flexibility needs to be maintained to ensure diversity in the participant sample.

Staff

The planned number of staff participants is 30 (5 staff from 6 sites) but we will allow flexibility within units, for example if one participant performs both selection and procurement.

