6.2 Recruitment

Patients

We will conduct interviews with patients from 6 hospitals. The PI and research team at each site will identify potential participants through the clinic list. Potential participants who require an endoscopy will be asked if they are interested in the study and given study documentation in person. Alternatively, patients can be sent an invitation letter, PIS and consent form via post and be given at least 24 hours to decide if they would like to take part.

Interested patients can contact the research team using the details provided in the study documents. Alternatively, they will be contacted after a reasonable amount of time has passed with no response to see if they are interested. If they agree to take part, consent will be obtained either in-person at attendance of the clinic, or via the telephone if necessary.

Staff

The PI and research team at each site will generate a list of all staff who work across the endoscopy pathway and identify potential study participants. Participants will be invited to take part in the study via email invitation along with the PIS from the site PI, or informed about the study in person and given a PIS.

Staff will have at least 24 hours to decide if they'd like to take part. If they agree, the PI and research team at site will then contact the member of staff to consent them in-person. Their contact details will be provided to the experienced qualitative researcher after consent who will then organise a focus group consisting of 2-5 members of staff on Microsoft Teams. However if this is not possible, an individual interview will be scheduled. Staff recruitment will continue until all segments of the extended endoscopy care pathway are accounted for, or when saturation is reached in the data collection.

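### The protocol states no comparison of staff by pathway role and does not list role among the staff data to be collected, although role shapes the objective and one of the two stopping conditions for staff recruitment

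*Protocol*

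**What the plan says.** Protocol 3.2 fixes the order of analysis: "Data from staff focus groups/interviews and patient interviews will be analysed separately, first by centre and then, by participant group". It does not define the participant groups. The only comparison it then describes is between patients and staff: "if appropriate, the patient and staff qualitative data will be compared, contrasted and combined, looking for consistencies and inconsistencies in the data and for deviant" …

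Elsewhere the protocol describes staff by what they do:

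- The primary objective (2.1) names staff who procure scopes, perform endoscopy, and clean and decontaminate. Section 1.3 gives a similar list: "e.g., selection, procurement, disinfection, and disposal of endoscopes".
- For recruitment (6.2), each site is to "generate a list of all staff who work across the endoscopy pathway and identify potential study participants". The stopping rule is: "Staff recruitment will continue until all segments of the extended endoscopy care pathway are accounted for, or when saturation is reached in the data collection".
- Section 6.1.1 allows flexible numbers within a unit when one person holds two roles. It also says that depth within each unit is not the aim.
- The results feed a logic model "which depicts the extended endoscope life cycle in the broad ecosystem beyond clinical care pathways" (1.2).

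Role is absent from two lists where one might expect it. The sampling plan in 6.1.1 is "maximum variation sampling based on the following parameters: age, ethnicity, gender for all participants, and years of experience for NHS staff". The staff descriptors in 7.1 are age group, sex, ethnicity and years of experience.

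**The concern.** Staff meet the scope at different points of its life, and the protocol uses those points to state its objective and to help decide when staff recruitment is complete. The analysis section then names centre and participant group as its units and does not return to role. A team that followed the text exactly would read five staff at a time by site, and then all staff together. A view held mainly by those who decontaminate scopes could then be reported as mixed opinion among staff, and it would be harder to place in a model laid out along the life cycle.

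The data-handling sections make this a matter of timing. If role is not attached to each speaker while the data can still be linked to a person, a later decision to compare roles may come too late.

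**Working it through.** **1. The plan's own figure.** Section 6.1.1 plans 5 staff from each of 6 sites: 5 × 6 = 30. This agrees with the stated 30. No power or error-rate calculation applies to a qualitative study.

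**2. People per segment.** The protocol does not say how many pathway segments there are. Let *k* be that number, assumed to lie between 3 and 6, and assume that segments are evenly filled. Then a centre holds 5/*k* staff per segment, and all sites pooled hold 30/*k*.

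| *k* (assumed) | Per segment within a centre, 5/*k* | Per segment pooled over sites, 30/*k* |
|---|---|---|
| 3 | 1.67 | 10 |
| 4 | 1.25 | 7.5 |
| 5 | 1.00 | 6 |
| 6 | 0.83 | 5 |

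With about one person per segment in a centre, a difference between roles cannot be told from a difference between individuals. Pooling by segment gives several people per role from the same 30. The left-hand column describes only the by-centre step. The next step, on the natural reading of 3.2, brings all 30 staff together without dividing them by role.

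**3. Whether the role label survives.** Set side by side:

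- 6.2: the site draws up the pathway staff list. After consent, the qualitative researcher is stated to receive contact details; role is not mentioned.
- 3.1: staff take part in online focus groups of 2–5 people, or in single interviews where a group is not feasible. The mix of roles in a group is not stated.
- 7.1: the listed staff descriptors omit role.
- 7 and 6.3: interview data are anonymised 7 days after the session. Sections 3.1 and 7.1 place anonymisation after transcription.
- 3.1: recordings are deleted once the transcript has been checked.

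Someone must track segments to apply the stopping rule in 6.2, so the information will exist at site. Nothing in the text carries it into the research dataset.

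**4. Who can fill the segments.** Section 2.1 includes staff who procure scopes, and 1.3 includes selection and procurement. Staff eligibility in 5.1 requires work in an endoscopy unit, with a primary role in performing endoscopy or in decontamination or disposal. Procurement is not named. Read literally, one role in the objective may have few or no eligible participants.

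**The case against.** A reader might infer that staff are recruited by segment, that this grouping is dropped at analysis, and that role differences can never be seen. The protocol does not support that reading.

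- **Recruitment.** Segment coverage is one of two alternative stopping conditions, the other being saturation, and role is not a named sampling parameter in 6.1.1.
- **Meaning of the second unit.** Because 3.2 already separates staff from patients, *participant group* could be read as groups within staff. The staff/patient reading is more natural, since the comparison described next is between those two, but the text is ambiguous and does not exclude role.
- **The question asked.** The objective is to explore views and experiences. It does not ask how they differ between roles. The logic model is a project-level output that other work packages also inform. That staff in different roles would be affected in opposite ways by single-use scopes is not stated anywhere.
- **The method.** Line-by-line thematic coding, progressive focusing and the search for inconsistencies and deviant cases could all bring out a role difference.
- **Centre.** Section 4 deliberately mixes tertiary centres with district general hospitals, so a by-centre reading is defensible.
- **The counts.** They depend on an assumed number of segments and an even spread, and no cell size is a threshold in thematic analysis.

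All of this stands and limits the point. It does not supply a definition of the second unit, a role label in the dataset, or a stated comparison by role. A role difference that emerges in coding can be attributed only if the speaker's role is known.

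**Conclusion.** The point holds as a gap in the stated plan and is worth closing because doing so is cheap. Section 3.2 states no comparison by pathway role and leaves its second unit undefined, and 7.1 does not provide for collecting the label that such a comparison would need. Role differences could still emerge; what is missing is provision for comparing them.

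The size is indicative only: about 1.7 to 0.8 staff per segment within a centre, against 10 to 5 pooled, for an assumed 3 to 6 evenly filled segments and the planned 30 staff. The conclusion does not depend on the exact number of segments. It rests on reading *participant group* as staff versus patients, and on the descriptor list in 7.1 being complete as written. If the sponsor meant staff subgroups, the definition and the role descriptor are still needed.

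**What to change.** Three changes to the text, made before data collection:

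1. **7.1:** add role or pathway segment to the staff descriptors, and attach it to each speaker before anonymisation. Allow two tags for staff with more than one role.
2. **3.2:** define *participant group*. State that staff data will also be synthesised by segment across centres and the segments compared, with the by-centre reading kept.
3. **5.1 and 2.1:** reconcile staff eligibility, which does not name procurement, with the objective, which does.

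No extra participants or sessions are needed. The costs are one added descriptor, with the matching change to data handling, and reliable attribution of speakers in focus groups. Some role cells will be small, so reporting by role must protect anonymity, particularly where a site has only one person in a role.

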4. STUDY SETTING

This study will be multi-centre, across 6 sites in England, Scotland and Wales. The only requirement for entry into the study is that the hospital site deliver endoscopy services.

Using professional networks and links with The British Society of Gastroenterology, gastroenterology units have been identified to participate in the study. Participants (staff and patients) will be sampled from those people who work in or access endoscopy services at these sites.

Some sites will be large tertiary centres which do complex endoscopic procedures, others will be District General Hospitals who do the vast majority of diagnostic endoscopies and the less complex therapeutic endoscopy. It is essential that ED&I is attended to in the selection of sites and participants to ensure a representative sample is obtained, and conclusions and recommendations can be drawn that are appropriate to the population in the UK. The aim will be for maximal variation in the sample, both in terms of the hospitals recruited (local population and geography) and the NHS staff and patients who are invited to participate (e.g., age, gender, ethnicity). The local population of the centres will include rural and urban areas with residents of mixed socioeconomic status.

5. ELIGIBILITY CRITERIA

5.1 Inclusion criteria

Patients

- Over the age of 18
- Patient has been invited to an NHS endoscopic clinic to undertake an upper GI endoscope procedure, including diagnostic endoscopies and the less complex therapeutic endoscopy.
- Patient is able to read and understand information provided
- Patient has capacity to provide consent
- Patient is able to participate in an interview.

Staff

- Over the age of 18
- Employed by the NHS
- Working in relevant endoscopy unit - primary work involves the conduct of endoscopy and/or waste disposal services (decontamination or disposal).

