6.3 Consent

Patients

Written consent will be obtained prior to interview by an appropriately trained and delegated member of the research team at each site. Telephone consent will only be obtained if the patient has already attended an endoscopy appointment and has no further appointments scheduled.

In person consent: If the patient has expressed an interest to take part in the study, consent will be obtained in person at the next clinic appointment.

Telephone consent: For patients who have already had their endoscopy, consent will be obtained via telephone. A member of the research team will confirm with the patient that they have read the PIS and consent form, and answer any questions. They will go through each clause of the consent form and document on the ICF by initialling each relevant box. They will then sign the consent form in place of the participant. The process must also be documented in the patient's medical notes including the study name, start and end time of the conversation, and specify which clauses of the consent they agree/disagree to.

Staff

If they have agreed to take part, staff will be consented in person at the site by the PI or member of the research team.

It will be explained to both sets that entry into the study is entirely voluntary and the right of a participant to refuse participation without giving reasons will be respected and recorded on the screening log. Participants can withdraw prior to, during or after the interview/focus group. They will have 7 days post-interview/focus group to withdraw their data from the study, before it is anonymised. Participants may be withdrawn from the study at the discretion of the investigator and/or co-investigators due to safety concerns. However, this is not anticipated to be an issue.

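### The patient reading requirement in section 5.1 makes no allowance for support and is not reconciled with the translation and interpretation promised in section 3.1

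*Protocol*

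**What the plan says.** The patient inclusion criteria in Protocol section 5.1 include "Patient is able to read and understand information provided". Capacity to consent and ability to take part in an interview are listed as separate criteria. No language is named, and nothing is said about help with reading.

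Section 3.1, under the patient interviews, states: "Translation and interpretation will be available for all persons who might not adequately understand verbal explanations". It gives the source of that help: "Translation and interpreters will be provided from across a network of support at UHCW and academic partners".

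On who should be in the sample, section 4 says "It is essential that ED&I is attended to in the selection of sites and participants to ensure a representative sample is obtained". Section 6.1.1 puts this into practice: "We will use maximum variation sampling based on the following parameters: age, ethnicity, gender for all participants". It also lets the plan of five patients per site bend, because "flexibility needs to be maintained to ensure diversity in the participant sample".

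Section 6.2 offers two routes of approach: documents handed over in person, or an invitation letter, information sheet and consent form sent by post. For consent by telephone, section 6.3 says "A member of the research team will confirm with the patient that they have read the PIS and consent form". Staff then answer questions and take the patient through the form clause by clause.

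**The concern.** Section 5.1 joins two requirements, reading and understanding, and a patient must meet both. Section 3.1 appears to expect that some participants will need language help. If a site screener applies section 5.1 as worded, a patient who cannot read the documents may be turned away before anyone considers the help in section 3.1.

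What is at stake is who enters the study. Section 1.2 wants to learn how the balance between infection control and environmental impact can be explained in forms people can use, and section 3.2 looks at how information for endoscopy patients could be improved. People who struggle with written information have direct experience of that question. Losing them through a line of eligibility wording would be avoidable selection. The six sites could also read the line differently, so that the same patient is accepted at one and refused at another.

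**Working it through.** No arithmetic applies. The check sets the provisions side by side.

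1. **Order of events.** Table 1 places the eligibility assessment at screening, and consent and the interview at Visit 1. The criterion is therefore applied before the consent conversation.

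2. **What each provision covers.** Section 5.1 concerns reading and understanding the information supplied. Section 3.1 is triggered by difficulty with spoken explanations. The two overlap but are not the same.

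3. **How four kinds of patient fare.**
   - *Reads the documents but needs help with speech, for example because of hearing loss or limited spoken English:* meets section 5.1 and can use section 3.1. No conflict.
   - *Reads another language and receives translated documents:* can read and understand what was provided. Both sections are met.
   - *Reads another language and receives untranslated documents:* fails section 5.1 as worded. The protocol speaks of translation in general but does not say that the information sheet, invitation letter or consent form will be translated.
   - *Cannot read in any language, or cannot see the text:* fails section 5.1 as worded, however well the patient understands the same content when it is spoken. Translated documents do not help.

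4. **Does data collection need reading?** Section 3.1 has patients interviewed by Microsoft Teams or telephone, with questions from a topic guide. Capacity and ability to be interviewed are already covered by their own criteria. As far as the interview is concerned, the reading requirement adds only a literacy filter.

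5. **Do the later steps repair it?** Section 6.2 relies on written documents and mentions no other format. Section 6.3 opens the telephone route by confirming that the patient has read the documents. The clause-by-clause review that follows is oral, so part of the remedy already exists. Neither section mentions an interpreter or reading the documents aloud.

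6. **Size.** The protocol gives no figure for patients who cannot read the documents. The only related number is the planned sample, 5 patients × 6 sites = 30, and it says nothing about how many would be excluded.

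**The case against.** The strongest case on the other side is that the two sections can both be followed. The criterion does not mention English, section 3.1 commits to translation as well as interpreters, and a patient given a translated sheet meets section 5.1. The participant documents are not part of the protocol text, so translated versions may exist. This stands, and three stronger readings fall with it or beside it.

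- A reader might infer that the sections flatly contradict each other, so that anyone needing an interpreter is ineligible. The first two kinds of patient in the check show otherwise, and no passage ranks one provision above the other.
- A reader might infer that the criterion removes the very people on whom the equality and diversity aim depends. The sampling parameters for patients are age, ethnicity and gender, and section 4 adds site population and geography. Language and literacy are not among them, and ethnicity does not stand in for inability to read the documents.
- A reader might try to put a number on the loss by assuming a share of non-readers and treating the 30 patients as random draws. The share would have no basis in the protocol, and sampling is purposive, so the result would not describe this study.

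It would also be wrong to say that telephone consent rests on reading alone, since questions are answered and each clause is gone through.

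The objection does not reach patients who cannot read at all or cannot see the text. Nor does it supply the missing statement of how section 3.1 support bears on section 5.1.

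**Conclusion.** The point holds as an unreconciled ambiguity with a real, limited consequence. Applied literally, section 5.1 excludes patients who cannot read in any language or cannot see the text. It may exclude those who cannot read the language supplied, depending on whether translated documents are provided. Both groups could include people able to understand the study orally and to be interviewed. That runs against the representative sample in section 4 and the interest in accessible communication in section 1.2.

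The conclusion assumes that sites apply the criterion as worded; a lenient site might not. The size of the subgroup is unknown. This is a qualitative study with no primary outcome measure, so no estimate is invalidated. Severity is moderate to minor: worth correcting, but not a condition for going ahead.

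**What to change.** Reword the criterion in section 5.1 along these lines: *Patient is able to understand the study information, in writing or verbally, with translation, an interpreter or read-aloud support where needed.*

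Then bring two later sections into line:

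- **Section 6.2:** say that the information sheet and consent form can be translated or read aloud, whether the approach is in person or by post.
- **Section 6.3:** let telephone consent accept that the documents were read either by the patient or to the patient, with an interpreter on the call where needed. The existing oral review of each clause stays as it is.

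The cost is a wording amendment and some longer, interpreted consent conversations and interviews, probably few in number. The translation and interpreter support is already promised in section 3.1.
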